**Per-Protocol Population:**

All subjects who have successfully completed all visits and did not substantially deviate from the protocol as determined by the trial cohort review committee prior to database hard lock (Per-Protocol Population). Justification of excluding subjects with protocol deviations in the per-protocol population set will be documented in a memo to file.

**Intent-to-Treat (ITT) Population:**

All randomized subjects regardless of actual treatment and subsequent withdrawal from study or deviation from protocol. At least one observation should be recorded.

#### **14.4. Level of Statistical Significance**

All planned analysis for this study will be conducted with an overall type I error rate of 5%.

#### **14.5. Primary Analysis**

Primary efficacy analysis:

Due to the potential low incidence rates of unacceptable lens fitting, summary statistics will be firstly used to evaluate the percentage of the subjects with at most one optimization per-protocol population.

Due to the potential low incidence rates of unacceptable lens fitting, summary statistics will be firstly used to evaluate the percentage of the subjects with at most one optimization per-protocol population.

If applicable, a generalized linear mixed model with a binary distribution and logit link function will be applied to the number of modifications (1=at most one modification; 0 = more than one modification). Age, gender and subjects' add power will be included in the model as fixed effects when appropriate. ECP and subject will be included as random effect.

The proportion of subjects with at most one optimization will be calculated with 95% confidence interval. If the lower limit of the confidence interval is greater than 50%, the statistical superiority will be concluded.

[REDACTED] (5)

If the incidence rate is too low or there are problems with the convergence of the above model, Agresti methods or Fisher's exact test for binomial proportion will be used to evaluate the confidence intervals of the corresponding endpoints.

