## SYNOPSIS

Protocol Title	Evaluation of the JJVC Investigational Toric Multifocal Contact Lens Fitting Guide Phase II
Sponsor	JJVC, [name]
Clinical Phase	Phase 2
Trial Registration	This study will be registered on ClinicalTrials.gov by the Sponsor
Test Article(s)	Investigational Products: etafilcon A Toric Multifocal Contact Lens Marketed Products: 1-Day Acuvue® Moist Brand Multifocal Contact Lens
Wear and Replacement Schedules	Wear Schedule: Daily Wear Replacement Schedule: None- Non-dispensing study
Objectives	The primary objective of this study is an evaluation of the JJVC Investigational Toric Multifocal and 1-Day Acuvue® Moist Brand Multifocal Contact Lens fitting guides by Eye Care Providers (ECPs).

[REDACTED] (5)

Study Endpoints	
Primary endpoint: The maximum number of lens modifications for both eyes required by the ECP to optimize the lenses for vision.
 
Secondary endpoint:
 
 
1. Subjective feedback from the ECP on the fitting guide process (i.e. intuitive nature of the fitting steps, adequate amount of information provided by the fitting guide, strengths and weaknesses, etc.)
 
2. Subjective feedback from the ECP regarding the layout of the fitting guide.
 
3. Surveys of the subjects experience.
 

Study Design	
This study is a single arm, non-randomized, open label, non-dispensing clinical trial. The key assessments for this study will be the number of fitting modifications and ECP feedback throughout the fit process while using the Fit Guide. Each ECP will fit at least 3 subjects and no more than 4.
 
See the flow chart at the end of the synopsis table for the schematic of the study visits and procedures of main observations.

Sample Size	
A total of approximately 32 subjects will be enrolled into the study. Approximately 24 are targeted to complete.

Study Duration	
The study duration is anticipated to be approximately 1 week.

Anticipated Study Population	
Healthy male and female volunteers with presbyopia will be screened as per criteria outlined below.

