#### **Other Observation(s)**

### **2.3. Hypotheses**

#### **Primary Hypotheses**

The maximum number of modification required by the ECP to optimize vision will not exceed one modification in more than 50% of the subjects.

Secondary Hypotheses  
Not Applicable

Other Hypotheses  
Not Applicable

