#### **4.3. Enrollment Target and Study Duration**

- Approximately 32 subjects will be enrolled in the study with 24 targeted to complete the cohort. An attempt will be made to recruit subjects that have -1.00D to -1.50D of refractive cylinder in at least one eye and no greater than -1.50D in either eye.
- The study will take place at one site and have one study visit per subject. Each ECP will fit a maximum of 4 subjects.

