## 14. STATISTICAL METHODS

### 14.1. General Considerations

All data summaries and statistical analyses will be performed using the SAS software Version 9.4 (SAS Institute, Cary, NC). Throughout the analysis of data, the results for each subject/eye will be used when available for summarization and statistical analysis. Unscheduled visits will be summarized separately and will be excluded from the statistical analysis.

Summary tables (Descriptive statistics and/or frequency tables) will be provided for all baseline variables, efficacy variables and safety variables as appropriate. Continuous variables will be summarized with descriptive statistics (n, mean, standard deviation (SD), median, minimum and maximum). Frequency count and percentage of subjects or eyes within each category will be provided for categorical data.

Summaries will be presented by study lens type and will be performed separately by completion status. All analyses will be conducted on per-protocol population (see section 14.3).

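### The primary model carries a subject random effect that one binary result per subject cannot support, the source of the deciding interval is not stated, and the fallback names two methods with no rule for choosing

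*Combined protocol and SAP*

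**What the plan says.** The Synopsis defines the primary endpoint as "The maximum number of lens modifications for both eyes required by the ECP to optimize the lenses for vision", which is one number per subject. The primary hypothesis in Section 2.3 is that the maximum "will not exceed one modification in more than 50% of the subjects". Section 4.3 fixes the number of observations: "The study will take place at one site and have one study visit per subject. Each ECP will fit a maximum of 4 subjects". The Synopsis adds "Each ECP will fit at least 3 subjects and no more than 4", so 24 completers means 6 to 8 ECPs.

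Section 14.5 begins with summary statistics. It then proposes, where applicable, a logistic mixed model for the indicator of at most one modification, with age, gender and add power as possible fixed effects, and "ECP and subject will be included as random effect". Next it says "The proportion of subjects with at most one optimization will be calculated with 95% confidence interval", and superiority is concluded if the lower limit exceeds 50%. If the rate is too low or the model does not converge, "Agresti methods or Fisher's exact test for binomial proportion will be used to evaluate the confidence intervals of the corresponding endpoints".

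Two other sections bear on this. Section 14.1 says that "the results for each subject/eye will be used when available for summarization and statistical analysis". Section 14.4 sets an overall type I error of 5% without stating sidedness.

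**The concern.** A random intercept describes correlation among repeated observations on the same unit. Here each subject supplies one 0/1, so nothing in the data separates subject variance from binomial variation. A proportion obtained by back-transforming the model intercept would then depend on a variance set by the software's algorithm, and Section 14.5 names no estimation method.

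The rest of the section does not settle which number decides the trial. It does not say whether the interval belongs to the raw proportion or to the model, whether a model estimate would be conditional or population-averaged, or at which covariate values it would be taken. It gives no criterion for when the model applies and no threshold for a rate that is too low. The fallback joins two methods with no order between them, and one of them compares groups. At a borderline count, the superiority conclusion could turn on a choice made after the data are seen.

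**Working it through.** **Inputs.** 24 completers and null value 50% (Synopsis, Sections 2.3 and 14.2); one binary result per subject (Synopsis, Section 4.3); 3 to 4 subjects per ECP (Synopsis); true rates of 70%, 75% and 80% (Section 14.2). Assumed here, because the documents do not give them: the illustrative counts 17, 18 and 19 of 24, the allocation of failures to ECPs, and an ECP intraclass correlation (ICC) of 0.10 to 0.20.

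**1. The plan's own power table.** Exact binomial test against 0.50:

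| True rate | n | Plan's power | One-sided 5% (needed; power) | One-sided 2.5% (needed; power) |
|---|---|---|---|---|
| 70% | 56 | 0.913 | 35; 0.9126 | 36; 0.859 |
| 75% | 35 | 0.924 | 23; 0.9244 | 24; 0.858 |
| 80% | 23 | 0.928 | 16; 0.9285 | 17; 0.840 |

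Only the one-sided 5% test reproduces the table. The lower limit of a two-sided 95% interval is a one-sided 2.5% rule, so Sections 14.2 and 14.5 match only if the interval in 14.5 is one-sided.

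**2. Subject random effect.** With intercept b and subject SD s, the marginal success probability is p(b, s) = ∫ expit(b + s·u) φ(u) du. The log-likelihood for x successes is x ln p + (n − x) ln(1 − p). For any s, b can be chosen so that p = x/n, so the maximum does not depend on s. At 19/24 it is 19 ln(19/24) + 5 ln(5/24) = −12.2818. With s fixed by hand:

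| Subject SD | Max. log-likelihood | Conditional proportion expit(b) | Its Wald 95% lower limit | Marginal proportion |
|---|---|---|---|---|
| 0 | −12.2818 | 0.792 | 0.587 | 0.792 |
| 1 | −12.2818 | 0.831 | 0.611 | 0.792 |
| 2 | −12.2818 | 0.896 | 0.654 | 0.792 |
| 4 | −12.2818 | 0.972 | 0.745 | 0.792 |

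What software reports depends on the algorithm. Restricted pseudo-likelihood converges to subject variance 0.256 and proportion 0.792. The Laplace approximation gives a log-likelihood of −12.28 at SD 0 and −11.39 at SD 4 (proportion 0.98), so it favours the larger SD for numerical reasons alone.

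Adding an ECP effect does not help. Over six assumed patterns of 5 failures (6 ECPs of 4 subjects, or 8 of 3), the maximised log-likelihood changes by at most 0.07 between SD 0 and SD 4 (largest change: −10.209 to −10.139). The population-averaged proportion changes by at most 0.003.

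**3. Fallback.** Agresti-Coull uses ñ = n + z² and p̃ = (x + z²/2)/ñ, with lower limit p̃ − z√(p̃(1 − p̃)/ñ). At 17/24, ñ = 24 + 3.8415 = 27.8415 and p̃ = (17 + 1.9207)/27.8415 = 0.6796, so the limit is 0.6796 − 1.96 × 0.0884 = 0.506. The exact (Clopper-Pearson) two-sided 95% lower limit is the 2.5th percentile of Beta(17, 8), which is 0.489. At 18/24 the limits are 0.548 and 0.533. The pseudo-likelihood model limit at 17/24 is 0.497.

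| Rule at n = 24 | Needed | Error at true 50% | Power at 70% | Power at 80% |
|---|---|---|---|---|
| Agresti-Coull | 17 | 0.032 | 0.565 | 0.911 |
| Exact, two-sided 95% | 18 | 0.011 | 0.389 | 0.811 |

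The rules differ only at exactly 17 of 24, which has probability 0.02, 0.18 and 0.10 at a true 50%, 70% and 80%. A one-sided exact 5% test, the basis of the power table, also needs 17.

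**4. ECP clustering.** Both fallback methods treat subjects as independent. Under a beta-binomial model at a true 50%, the one-sided error is:

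| ICC | ECPs × subjects | 17 or more | 18 or more |
|---|---|---|---|
| 0.10 | 8 × 3 | 0.046 | 0.019 |
| 0.10 | 6 × 4 | 0.053 | 0.023 |
| 0.20 | 8 × 3 | 0.060 | 0.028 |
| 0.20 | 6 × 4 | 0.074 | 0.037 |

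The reference value is 0.025 for a two-sided 95% interval, or 0.05 on the power table's basis.

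**The case against.** The random effect has little influence on the decision. Conditional and population proportions coincide at 50%. In exact-likelihood fits of the intercept-only model, 16/24 fails at every subject SD from 0 to 4 (lower limits 0.461 to 0.405) and 17/24 succeeds at every one (0.502 to 0.520). Only the pseudo-likelihood fit at 17/24 goes the other way. The range 0.79 to 0.97 comes from SDs fixed by hand, and the one fit run to convergence returns 0.792, close to the raw proportion. All of this stands, and it limits the first defect mainly to the reported estimate and interval.

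Section 14.1 permits eye-level data, and Section 2.2 words the endpoint as a number of lenses with no per-subject maximum. With two rows per subject, a subject term would be the natural choice. But the Synopsis endpoint, the hypothesis and the proportion in Section 14.5 are all per subject, so an eye-level model would estimate something else. If eyes were intended, the plan needs correcting in a different place.

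The convergence fallback does imply that the main interval was meant to come from the model, and it may catch a failed fit. It does not catch an algorithm that converges on an arbitrary variance.

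The fallback conflict is also narrow. It concerns one count at n = 24; it recurs at n = 22, 27, 29, 31 and 32 but not at 23, 25, 26, 28 or 30. The per-protocol number is not fixed in advance, so the conflict cannot be assumed away. Finally, this is a small single-arm fitting study not sized on power. That bears on the weight of the point, but the plan still makes a formal superiority claim from this interval.

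**Conclusion.** The concern holds. On the documented subject-level endpoint, the subject variance is not identifiable and the term should not be in the model. The interval that decides superiority has no stated source. The fallback is wrong as written, because it includes a test that gives no interval for a single proportion and sets no rule between its two options.

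The consequence for the decision is confined to borderline counts: at 24 completers, a result of 17 is a success or a failure depending on the method, with probability 0.18 at a true 70% and 0.10 at 80%. The consequence for the reported estimate can be larger if a conditional model proportion is used.

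This rests on three assumptions: one row per subject, Clopper-Pearson as the interval meant by the exact option, and a two-sided 95% interval. The clustering error rates rest also on the assumed ICC. This should be fixed before database lock; it does not call the study design into question.

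**What to change.** Change Section 14.5 as follows.

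- State that the unit of analysis is the subject, and delete the subject random effect.
- Define the primary estimate as the subject-level (population) proportion with at most one modification. Name one interval and its sidedness, and align this with Sections 14.2 and 14.4.
- Drop the choice between two fallback methods. If an exact method is meant, replace Fisher's exact test with the exact binomial (Clopper-Pearson) interval.
- Pre-specify, as a sensitivity analysis, a population-averaged analysis clustered by ECP only, with a small-sample correction. With 6 to 8 ECPs it will be imprecise.
- Make the model with age, gender and add power supportive only.

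The cost is SAP wording, with no new data. The choice of interval is the sponsor's. At 24 independent subjects, the two-sided 95% exact interval needs 18 successes instead of the 17 that Agresti-Coull needs, and power falls from 0.911 to 0.811 at a true 80% and from 0.565 to 0.389 at 70%. Agresti-Coull avoids that loss but has a one-sided error of 0.032, above the 0.025 implied by a two-sided 95% interval.

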#### **14.6. Secondary Analysis**

This is not applicable.

#### **14.7. Other Exploratory Analyses**

This is not applicable.

#### **14.8. Interim Analysis**

This not applicable.

#### **14.9. Procedure for Handling Missing Data and Drop-Outs**

Missing or spurious values will not be imputed. The count of missing values will be included in the summary tables and listings.

Subject dropout is expected to be one of the main reasons of missing data in this clinical trial. Past clinical trials don't provide the evidence that subject dropout is systematic or not-at-random. To evaluate the impact of missing data, sensitivity analysis will be conducted using multiple imputation methods if the proportion of subject dropout is greater than the 15%. The SAS/STAT procedures PROC MI and PROC MIANALYZE will be utilized with a parametric regression method used to make at least 5 imputations.

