### **8.2. Withdrawal/Discontinuation from the Study**

A subject will be withdrawn from the study for any of the following reasons:

- Subject death during the study period
- Subject withdrawal of consent
- Subject not compliant to protocol
- Subject lost to follow-up
- Subject no longer meets eligibility criteria (e.g. the subject becomes pregnant)
- Subject develops significant or serious adverse events causing discontinuation of study lens wear
- Subjects who have experienced a Corneal infiltrative Event (CIE)
- Investigator's clinical judgment regarding the subject safety reasons (that it is in the best interest of the subject to stop treatment)
- Subject not compliant with study lens wear schedule
- Subject not successfully dispensed due to lack of efficacy and safety including poor vision, poor comfort or unacceptable fit

For discontinued subjects, the Investigator will:

- Complete the current visit (scheduled or unscheduled)
- Complete the Final Evaluation, indicating the reason that the subject was discontinued from the study
- Record the spherocylindrical refraction with best corrected distance visual acuity
- Collect used Test article(s) (worn or brought to the visit) from the subject and discard them, unless otherwise stated in Section 7.2
- Collect all unused Test article(s) from the subject

An additional subject may be enrolled if a subject discontinues from the study prematurely.

In cases where a subject is lost to follow-up, every possible effort must be made to contact the subject and determine the reason for discontinuation/withdrawal. The measures taken to follow up must be documented including two written attempts and a certified letter (or equivalent) as the final attempt.

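### The dropout sensitivity analysis in 14.9 is assigned no population that contains dropouts, and its imputation model is not specified for the binary endpoint

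*Combined protocol and SAP*

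**What the plan says.** - **Trigger and method (14.9).** The section opens by stating that missing values are not to be imputed. It then plans a multiple-imputation sensitivity analysis "if the proportion of subject dropout is greater than the 15" per cent, using PROC MI and PROC MIANALYZE with "a parametric regression method used to make at least 5 imputations". It names no imputed variable, no covariates and no analysis set.
- **Expected loss (4.3).** "Approximately 32 subjects will be enrolled in the study with 24 targeted to complete the cohort". Section 14.2 gives the same enrolment and treats 24 as a minimum. Section 8.2 allows discontinued subjects to be replaced.
- **Analysis set (14.1).** "All analyses will be conducted on per-protocol population". Section 14.3 limits that set to subjects who finished all visits without substantial deviation.
- **ITT set (14.3).** "All randomized subjects regardless of actual treatment and subsequent withdrawal from study or deviation from protocol". Section 5.3 says there is no randomization.
- **Safety set (14.3).** Everyone given a test article, with at least one observation.
- **Endpoint and criterion (14.5).** The outcome is coded 1 for at most one modification and 0 for more than one, with a logit model. "If the lower limit of the confidence interval is greater than 50%, the statistical superiority will be concluded".
- **Withdrawal reasons (8.2).** These include: "Subject not successfully dispensed due to lack of efficacy and safety including poor vision, poor comfort or unacceptable fit".

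**The concern.** This is the only analysis planned to test whether dropout changes the answer. If the plan is followed literally, it runs on a set from which dropouts have been removed by definition, so it has nothing to fill in.

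If the programmer picks a wider set, the plan does not say which one, or which model suits a 0/1 outcome. Whatever the model, imputing from completers assumes that dropouts resemble completers. That is doubtful here, because 8.2 removes subjects for poor vision, poor comfort or unacceptable fit. Some of these reasons are close to the endpoint itself, which is how many changes are needed to optimize vision. A reader of the report could see a reassuring sensitivity result that never addressed the subjects in question.

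**Working it through.** **1. Which set could the analysis use?**

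| Set | Definition in 14.3 | Contains fitted dropouts? | Assigned to 14.9? |
|---|---|---|---|
| Per-protocol | Completers without substantial deviation | No, by definition | Yes, through 14.1 |
| ITT | Randomized subjects | Empty: 5.3 says no randomization | No |
| Safety | Anyone given a test article, with an observation | Yes | No |

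Section 8.1 counts as complete only subjects not withdrawn for an 8.2 reason. A subject withdrawn for poor vision or unacceptable fit therefore cannot be per-protocol. Outcomes missing through dropout in the assigned set: 0.

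**2. Is the trigger likely to be met?** The allowance is (32 − 24)/32 = 8/32 = 25.0%. The rule needs more than 15% of 32: 4/32 = 12.5% does not fire and 5/32 = 15.6% does. With X ~ Binomial(32, d), for assumed true dropout rates d:

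| d | P(X ≥ 5) |
|---|---|
| 10% | 0.21 |
| 15% | 0.54 |
| 20% | 0.80 |
| 25% | 0.93 |

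**3. Does the handling of dropouts matter?** The plan's own power table (14.2) reproduces with an exact binomial test against 50% at one-sided 0.05: 0.9126, 0.9244 and 0.9285 for N = 56, 35 and 23, against the stated 0.913, 0.924 and 0.928. So the exact binomial is a fair basis for illustration. For the 14.5 criterion I take the 95% interval as two-sided. The exact lower limit for x successes in n is the 2.5% quantile of Beta(x, n − x + 1). The completer results and the number of dropouts counted as failures are assumptions, because the documents give no split of dropout reasons.

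| Completers | Dropouts counted as failures | x/n | Exact 95% lower limit | Above 50%? |
|---|---|---|---|---|
| 20/24 | 0 | 20/24 | 62.6% | Yes |
| 20/24 | 4 | 20/28 | 51.3% | Yes |
| 20/24 | 5 | 20/29 | 49.2% | No |
| 18/24 | 0 | 18/24 | 53.3% | Yes |
| 18/24 | 2 | 18/26 | 48.2% | No |

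As outer bounds with all 8 missing, 18/24 becomes 18/32 (37.7%) if all are failures and 26/32 (63.6%) if all are successes.

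**4. Does the interval method matter?** Section 14.5 names a model-based interval first, with Agresti or exact methods as fallback. Two checks on the number of failures needed to reverse the result:

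- Agresti-Coull: p̃ = (x + 1.96²/2)/(n + 1.96²), lower limit p̃ − 1.96·√(p̃(1 − p̃)/(n + 1.96²)). 20/29 gives 50.6% and 20/30 gives 48.7%, so six are needed. 18/25 gives 52.2% and 18/26 gives 49.9%, so two are needed.
- Exact limit at one-sided 5%: 20/30 gives 50.1% and 20/31 gives 48.2%, so seven are needed. 18/26 gives 51.3% and 18/27 gives 49.1%, so three are needed.

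The reversal point moves, but stays within the 8 planned losses in every case.

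**The case against.** Five points can be made for the plan.

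- **The method may be adequate.** A reader might infer that 14.9 imposes a normal linear model on a 0/1 outcome. The text does not say so. Logistic regression is also parametric, and 14.5 already uses a logit model for this outcome. Even under a normal model the damage is small: in simulation with 24 observed and 8 missing, rounding lowered the imputed success rate by about 3 points. Over 32 subjects that is 3 × 8/32, under 1 point. This objection stands: the defect is an unspecified model.
- **A population does exist.** A reader might infer that no set could hold the dropouts. The Safety set could. What remains is that 14.9 does not name it and 14.1 directs all analyses elsewhere.
- **The trigger may not be met.** The 25% is an allowance: the numbers are approximate, 24 is a minimum in 14.2, replacement is allowed, and some losses may come before any lens is inserted. Likely is supported; certain is not.
- **Counting fit failures changes the question.** Steps 1.20 and 1.21 remove unacceptable physical fits before the vision modifications of steps 1.23 and 1.24. This is right, so such an analysis must be labelled a composite. It does not justify leaving these subjects out of every analysis.
- **The sponsor has a stated position.** Section 14.9 says past trials give no evidence of systematic dropout. But 14.2 says no earlier study evaluated the number of modifications, so that history cannot settle the matter for this endpoint.

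**Conclusion.** The point holds in this form: followed as written, the 14.9 analysis has no outcomes lost to dropout to impute, because its only assigned set excludes dropouts and the ITT set is empty as worded. The model is also unspecified for a binary outcome, and the section's opening sentence conflicts with its own plan unless it is limited to the main analysis.

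The size is conditional. The trigger is met with probability 0.93 if true dropout is 25%, and 0.54 if it is 15%. With 20/24 successes, five dropouts counted as failures reverse the conclusion on the exact 95% limit; with 18/24, two do. These reversals rest on assumed dropout reasons and measure the effect of how dropouts are counted. They do not measure the effect of choosing one imputation model over another.

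The documents do not support saying that a normal model is prescribed, that no usable set is defined anywhere, or that the trigger is bound to be met. The primary per-protocol analysis can still be run as planned; what fails is the check on it.

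**What to change.** 1. In 14.3, redefine the ITT set as all subjects in whom a study lens was inserted, without reference to randomization. Assign the 14.9 sensitivity analysis to it, and state the exception in 14.1.
2. Add a sensitivity analysis that counts subjects discontinued for unacceptable fit, vision or comfort as not meeting the endpoint. Report it beside the per-protocol result, and label it a composite because physical fit is judged before any vision modification.
3. For other missing outcomes, name the binary endpoint as the imputed variable and use a logistic imputation model with few, stated covariates. If the model separates, use a penalised fit or simple best-case and worst-case bounds.
4. State that the opening sentence of 14.9 applies to the main analysis only.

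More imputations than five, or running the analysis whatever the dropout rate, would be reasonable preferences but are not needed to repair the plan.

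The cost is SAP wording and minor programming. The sensitivity estimate may be less favourable than the per-protocol one. Logistic imputation may also be unstable with few failures: 20/24 leaves only four.
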